MonaLisa Touch CO₂ fractionated laser is a novel, minimally invasive therapy that helps restore vaginal health. The U.S. Food and Drug Administration (FDA) approved the technology for the excision, vaporization, and ablation of tissues and since then it has been used in many different fields of medicine⁶, but it is not approved for the treatment of vulvovaginal atrophy or GSM at the present time. Though observational studies show a possible benefit of MonaLisa Touch in the treatment of vulvovaginal atrophy and GSM^{7,8,9,10}, no studies with long-term follow-up have been performed to date.

We propose a prospective case series of 15 postmenopausal women with bothersome symptoms of GSM treated with MonaLisa Touch CO₂ laser. We hypothesize that even in the long term MonaLisa Touch will significantly improve GSM histologically and clinically from baseline.

Inclusion Criteria:

- Italian speaking and able to give informed consent.
- Menopausal females with absence of menstruation for at least 12 months.
- Presence of GSM symptoms.
- Completion of at least two cycles of three laser treatments sessions in previous years.
- Prolapse stage < II, according to the pelvic organ prolapse quantification (POP-Q) system.
- No pelvic surgery within 6 months prior to treatment.
- Understanding and acceptance to the obligation to return to all scheduled visits and follow-ups.

Exclusion Criteria:

- Inability of give informed consent
- History of vulvovaginal condyloma, vaginal intraepithelial neoplasia (VAIN), vaginal carcinoma, lichen sclerosis, lichen planus.
- History of cancers of the lower genital tract (cervix, uterus, vagina).
- History of pelvic radiotherapy.
- Personal history of genital fistula, a thin recto-vaginal septum as determined by the investigator or personal history of a fourth degree laceration during screening physical exam.
- Any other medical condition that the investigators feel would compromise the study.
- Acute or recurrent urinary tract infection (UTI), or genital infection (e.g. bacterial vaginosis, herpes genitalis, candida).
- Stage III or IV pelvic organ prolapse.
- History of any female sexual disorder.

Power analysis: As this is a prospective case series, no formal power analysis is required.

Efficacy Outcomes:

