The **primary outcome objective of the study** is to evaluate the histological modifications of the vaginal mucosa after repeated CO₂ Monalisa Touch laser treatment. We shall evaluate the role of this treatment by calculating the difference in vaginal epithelial thickness between the biopsy obtained before the start of laser treatment and the biopsy obtained after treatment. The latter parameter will be calculated by averaging three measurements 150 micrometers from each other and considering as significant a 20% increase in epithelial thickness compared to baseline. We will then compare the number of papillae, the amount of glycogen present at the epithelial level (by PAS reaction), the ratio between the number of type I collagen fibers ("new" collagen) and type III (old collagen), and the number and size of the vessels present in the subepithelial layer. In addition, the study will analyze the safety of repeated laser treatments verifying the absence of fibrosis formation in the vaginal mucosa.

Secondary objectives of the study will include an evaluation of the clinical effects associated with repeated Monalisa Touch CO₂ laser treatments. Questionnaires to address these secondary objectives will include the following:

- Vaginal Health Index (VHI)¹¹ which will objectively measure the severity of vaginal atrophy
- Visual Analog Scale (VAS) which will subjectively measure the severity of vaginal symptoms
- Female Sexual Function Index (FSFI)¹² questionnaire which will assess female sexual function
- Urinary Distress Inventory-6 (UDI-6) and the International Consultation on Incontinence Questionnaire – Urinary Incontinence (ICIQ-UI) which will evaluate the extent of urinary symptoms
- 5-point Likert¹³ scale to assess the impact of GSM symptoms on quality of life (QoL)

Study Design: All participants will be screened to ensure inclusion/exclusion criteria are met. A biopsy will be taken from each patient one month before the first laser treatment and one month

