after the last laser treatment. The MonaLisa treatment will be performed monthly for 3 months. MonaLisa treatment with fractional microablative laser system (SmartXide 2 V 2 LR, MonaLisa Touch, DEKA, Florence, Italy) will be performed to the following energy settings and treatment parameters: dot power 30 W, dwell time 1000us, dot spacing 1000um, smart stack parameter from 1 to 3 and emission mode deka pulse. For subjects with concomitant vulvar symptoms, vulvar treatment will be done with the dot power reduced to 26 W, dwell time 800us, dot spacing 800um, and the smart stack parameter of 1.

During the procedure, an external introducer ring will be inserted into the vaginal canal, the markings on the probe will be aligned with the edge of the ring to measure withdrawal of the probe after a series of pulses will be delivered, and the probe will be rotated of 60°. Laser power could be adjusted before and during the treatment to assure patient comfort. The procedure will be performed in the outpatient clinic, not requiring any specific preparation, analgesia, or anesthesia. Participants will be advised to refrain from engaging in sexual intercourse or bathe for 48 hours after the MonaLisa treatment.

Biopsy samples will be analyzed with Hematoxylin- Eosin and Trichrome staining, PAS reaction for glycogen and immunohistochemistry for CD34, a vessel marker. All clinical questionnaires and VHI will be assessed at baseline and at one month after the last session.

Any medical changes will be reported to the research team who will then evaluate for any impact on the study. Any adverse effects reported by participants will also be recorded and managed accordingly.

Fifteen subjects will be considered for the study. All materials will be kept confidential and maintained by the research coordinator in a locked cabinet.

The participants will keep the research team aware of any changes in medical history, and if any adverse effects are detected.

Data Collection:

- Biopsy baseline visit -Visit 1:
 - Inclusion/Exclusion criteria;

- Collection of patient anamnestic information (age, parity, years since menopause, previous pathologies, previous surgical interventions, BMI, use of estrogenic therapies, sexual activity);
- VAS, FSFI, ICIQ-UI, UDI6 e Likert questionnaires completion;
- Informed Consent signing;
- Bioptic procedure;
- VHI completion from research coordinator;
- Laser treatment visits (three visits at one month interval) - Visit 2, 3, 4

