 - Monalisa Touch Laser procedure
 - Adverse events including inability to complete the procedure due to discomfort or constricted vagina.
- Follow-up visit (1 month from the last laser treatment) – Visit 5
 - VAS, FSFI, ICIQ-UI, UDI6 e Likert questionnaires completion;
 - Bioptic procedure;
 - VHI completion from research coordinator;

Data Management: To ensure the protection of each subject's personal health information (PHI), one master Excel file containing subject PHI including name and medical record number will be kept on a password-protected and SharePoint computer. The participant shall be given a unique identification number used for the purpose of de-identified data collection and analysis.

Any hard-copy forms for data collection will be kept in a locked cabinet in the PI's office, which shall be locked at all times, at Urogynecology department at Ospedale San Raffaele Milan, Italy. All forms will contain de-identified information. Identification numbers will correspond to the subjects listed in the master Excel file.

Summary: GSM is a progressive and devastating condition in menopausal women, and is associated with bothersome irritative symptoms compromising the quality of life if this population. MonaLisa Touch laser treatment has shown initial promise in reversing postmenopausal vaginal atrophy, but its efficacy in treating symptoms of GSM long term is lacking. This study is designed

to investigate the long term feasibility of using Mona Lisa laser therapy to treat GSM symptoms in postmenopausal women.

References:

-
- ¹ Cagnacci A, Xholli A, Sclauzero M, et al. Vaginal Atrophy across the Menopausal Age: Results from the ANGEL Study. *Climacteric*. 2019;22(1):85-89.
 - ² Fadare O et al. The Spectrum of Morphologic Alterations Associated With Infarction in Endometrial Polyps: A Report of 41 Cases. *Int J Gynecol Pathol*. 2017.
 - ³ The North American Menopause Society. Management of Symptomatic Vulvovaginal Atrophy: 2013 Position Statement of The North American Menopause Society. *Menopause*. 2013;20:888-902.
 - ⁴ Shulman LP, Portman DJ, Lee WC, et al. A Retrospective Managed Care Claims Data Analysis of Medication Adherence to Vaginal Estrogen Therapy: Implications for Clinical Practice. *Journal of Women's Health* (2002) 2008;17:569-78.
 - ⁵ Faubion SS, Sood R, Kapoor E. Genitourinary Syndrome of Menopause: Management Strategies for the Clinician. *Mayo Clin Proc*. 2017;92(12):1842-1849.

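### Visit 5 has no adverse-event item, and the fibrosis aim, if read as a conclusion about the treatment, claims more than 15 women can show

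*Protocol*

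**What the plan says.** **Safety aim.** After describing the histological comparisons, Efficacy Outcomes adds that "the study will analyze the safety of repeated laser treatments verifying the absence of fibrosis formation in the vaginal mucosa". It states no tolerable rate or margin.

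**Sample size.** Study Design says "Fifteen subjects will be considered for the study", and the Power analysis paragraph says "As this is a prospective case series, no formal power analysis is required".

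**Earlier laser exposure.** One inclusion criterion is "Completion of at least two cycles of three laser treatments sessions in previous years".

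**Biopsies.** Study Design says "A biopsy will be taken from each patient one month before the first laser treatment and one month" after the last one. It also says "Biopsy samples will be analyzed with Hematoxylin- Eosin and Trichrome staining", together with a glycogen reaction and a vessel marker, and does not restrict the stains to one visit.

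**Adverse events.** Data Collection lists for the laser visits (2, 3 and 4) "Adverse events including inability to complete the procedure due to discomfort or constricted vagina". For Visit 5, one month after the third session, it lists the questionnaires, the biopsy and the VHI. No later visit is scheduled. Study Design has two provisions that are not tied to any visit. One is "Any adverse effects reported by participants will also be recorded and managed accordingly". The other asks participants to tell the research team of health changes and of any adverse effects.

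**The concern.** The study makes the safety of repeated laser treatment an explicit aim, and two parts of the Protocol serve that aim poorly.

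The first is the visit list. In the month after the third session, staff following the list would complete five questionnaires, a biopsy and the VHI without being prompted to ask about adverse events. An event the woman does not raise herself could go unrecorded.

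The second is the wording on fibrosis. If no biopsy shows fibrosis, the sentence lets a report say that absence was verified, although the data would still be compatible with a true rate of about one woman in five. The Protocol's own background says that the device is not approved for this condition and that no long-term studies exist, so an overstated safety result would matter.

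**Working it through.** **Part 1: the visit list.** The scheduled contacts in Data Collection compare as follows.

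- Visit 1: eligibility, history, questionnaires, consent, biopsy, VHI. No laser session yet.
- Visits 2, 3 and 4: laser session and an adverse-event item.
- Visit 5: questionnaires, biopsy, VHI. No adverse-event item.

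The number of scheduled contacts after the third session is 1, and the number of those with an adverse-event item is 0. What remains for that month is the two provisions in Study Design, and both depend on the participant speaking up.

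**Part 2: what 15 women can show about fibrosis.** There is no calculation in the Protocol to reproduce, because 15 is stated without one. The inputs are n = 15 (Study Design), a zero count (the result most favourable to the aim) and, as an assumption, a range of true rates p, since the Protocol gives none.

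The exact (Clopper-Pearson) upper limit for 0 of n is 1 − 0.025^(1/n) for a two-sided 95% interval and 1 − 0.05^(1/n) for a one-sided 95% limit.

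- 0 of 15, two-sided: 1 − 0.025^(1/15) = 0.218, so the interval is 0 to 21.8%.
- 0 of 15, one-sided: 1 − 0.05^(1/15) = 0.181, or 18.1%.

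The chance that 15 women show no case is (1 − p)^15.

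- p = 5%: 0.95^15 = 0.463
- p = 10%: 0.90^15 = 0.206
- p = 15%: 0.85^15 = 0.087
- p = 20%: 0.80^15 = 0.035

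If some women lack an evaluable pair of biopsies, the two-sided limit for a zero count rises. The Protocol gives no figure for such losses, so these are assumptions: 23.2% for 0 of 14, 24.7% for 0 of 13 and 26.5% for 0 of 12.

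**Part 3: which sessions the two biopsies span.** Sessions before the Visit 1 biopsy are at least 2 cycles × 3 = 6. Sessions before the Visit 5 biopsy are at least 6 + 3 = 9. The comparison between the two biopsies therefore covers only the current cycle of three. Fibrosis found at Visit 5 by itself would reflect all nine or more sessions and whatever preceded them. No biopsy before the earlier cycles is planned, so fibrosis at Visit 1 has no untreated reference.

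**The case against.** The best reply is that this is a descriptive case series. In a biopsy study, verifying that fibrosis is absent can simply mean checking the specimens for it. On that reading the aim can be met: 15 pairs can be examined and the result reported. The Protocol sets no margin or test and states no conclusion for a wider population, and exact intervals are commonly left to a statistical analysis plan, which is not shown here. Much of this stands. The size of the study is not at fault, and waiving a power calculation is acceptable. What remains is that the objective is worded in the Protocol, names its own outcome and attaches it to the safety of the treatment, so the wording still permits the stronger claim.

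On Visit 5, one can say that the two provisions in Study Design apply throughout, and that the visit is in person with questionnaires on vaginal, urinary and sexual symptoms. That is right, and a reader who inferred that events after the third session are not recorded at all would go too far. But those questionnaires measure efficacy and are not an adverse-event enquiry, so the gap in the list remains. Nor do the documents show that the first two sessions are followed up better than the third, because the item at Visits 2 to 4 may be meant for the procedure day only.

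A reader might also infer that fibrosis will be judged only as change between the two biopsies, so that fibrosis from earlier cycles is left out by design. The Protocol does not say so. The word for formation might suggest it, but the word for absence fits a direct reading of the Visit 5 biopsy equally well, and the stains apply to the biopsy samples in general.

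**Conclusion.** The point holds in two limited parts.

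1. Visit 5, the only scheduled contact after the third session, has no adverse-event item. Events in that month are captured passively. This follows from the visit list and rests on no assumption about rates.
2. If the fibrosis aim is read as a conclusion about the treatment, 15 women cannot support it. The most favourable result, 0 of 15, leaves a true rate of up to 21.8% possible (two-sided 95%), and a true rate of 10% would be missed altogether about one time in five. These figures assume that all 15 women are evaluable and independent, with a yes-or-no call on fibrosis. The rates of 5% to 20% are illustrative.

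The history of at least six earlier sessions is a limit on interpretation that should be stated with the results. It does not show that the biopsies will be read wrongly. The calculation is not a case for enrolling more women, and the primary outcome on epithelial thickness is unaffected.

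**What to change.** **Visit 5.** Add one item to the list: *Adverse events since the last laser session*. Leave out the wording about being unable to complete the procedure, since no procedure with the laser takes place at that visit.

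**Safety aim.** Keep the objective, and replace its closing clause with *by estimating the frequency of fibrosis in the vaginal mucosa on the Visit 1 and Visit 5 biopsies*. Report three counts, each over the number of evaluable women and with an exact (Clopper-Pearson) 95% CI:

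- women with fibrosis present at Visit 1;
- women with fibrosis present at Visit 5;
- women with fibrosis absent at Visit 1 but present at Visit 5, among those with both biopsies evaluable.

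Use the stains already planned. A count of worsened fibrosis should not be added unless a grade is defined, because the Protocol gives none.

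**Interpretation.** State that every woman had at least six sessions before the Visit 1 biopsy, that the paired comparison therefore covers only the current cycle, and that fibrosis at Visit 1 cannot be attributed to the laser.

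**Cost.** One reworded sentence, one statement on interpretation, a present-or-absent entry for each existing biopsy and one extra item on the Visit 5 form. No women, visits, biopsies or stains are added. The downside is a weaker safety statement than the present wording allows.
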